## **VI. Subject Accountability**

### **A. Demographics and Baseline Characteristics**

Data collected on the following characteristics at Screening or Baseline will be summarized in a table presented in a listing by actual treatment group for all randomized subjects:

- Age (Age will be calculated as the number of years elapsed between birth date and the date of the screening visit, adjusted for whether the birthday has passed as of the final day of the screening visit).
- Age categories (<65 vs. >=65) and (<75 vs. >=75)
- Sex
- Ethnicity
- Race
- Height (cm)
- Weight at baseline (kg)
- Body Mass Index (BMI) at baseline: Calculated as the individual's body mass (kg) divided by the square of their height (m) with the unit of kg/m^2
- Time from NYHA Diagnosis to Informed Consent (months): calculated as (NYHA Diagnosis Date – Informed Consent Date) / 30.417
- NYHA Class of HF Diagnosis at baseline

Demographic and baseline characteristic data will also be presented in a by-subject listing.

## **B. Disposition**

The summary table of subject disposition will include all screened subjects and display the following by treatment (if applicable):

- Number of subjects who screened
- Number and percentage of subjects who failed screening with the failed inclusion/exclusion criteria as the reason of screen failure
- Number of randomized subjects
- Number and percentage of randomization failures, using the number of randomized subjects as denominator for the percentages. Randomization failure subjects are those that passed initial screening assessments and were randomized into the trial but failed out on Day 1 due to any Day 1 labs/assessments making them ineligible (e.g., they had become pregnant, lab values were unacceptable per exclusion criteria, any morning test results were exclusionary).

Subjects who discontinued the study with discontinuation reason = “Randomization Failure” on the Study Discontinuation Form will be counted as randomization failures in the summary.

- Number and percentage of subjects in each analysis population, using the number of randomized subjects as denominator.
- Number and subjects discharged later than Day 3.
- Study completion status (completed or permanently discontinued). List the number and percentage of subjects for each reason of discontinuation, using the number of randomized subjects as denominator for the percentages.
- Number of days in the study among the randomized subjects, calculated as: End of Study Date (completion or discontinuation) – IP administration date + 1.

The following termination reasons as recorded on the End of Study form will be considered:

- Adverse event
- Death
- Lost to follow-up
- Physician decision
- Study terminated by sponsor
- Subject non-compliance/protocol violation
- Withdrawal of consent

A listing will present subject enrollment, with the protocol version for which subject was enrolled, and the inclusion in each analysis population.

A separate listing by subject will display the details of screen failure reason of each subject.

A by-subject listing will display subject disposition. All randomized subjects will be included.

### **C. Protocol Deviations**

Protocol Deviations will be summarized with number (and percentage) of subjects in each protocol deviation category in a table by treatment and cohort. Minor and major deviations will be displayed separately. In addition, a listing will be presented for subjects with protocol deviations, with the date of screening, sentinel or randomized, date of randomization (if applicable), cohort, treatment received (if applicable), and details of protocol deviation.

## **VII. Safety Analyses**

All safety analyses will be performed on the Safety Evaluation Population. Analyses specific to DLAEs will use the DLAE Evaluation Population. The subjects given placebo are also included specifically to compare against JK07 such that the background disease from the treatment effects in the study population may be assessed and better discerned. All safety data will be evaluated based on Common Terminology Criteria for Analysis Events (CTCAE) Version 5.0, and listed by cohort, subject, and visit. Categorical data will be summarized in count and percentage by cohort and category.

For laboratory test results, vital signs, ECG results, weight, and body mass index (BMI), observed values and change from baseline (CFBL) will be summarized by cohort and visit using descriptive statistics.

### **A. Exposure**

Exposure to study treatment (JK07 or Placebo) will be listed by subject and will present the planned dose and actual dose (including units), and the date and time of infusion, and interruption and the reason for interruption (if applicable).

## **B. Adverse Events**

An adverse event (AE) is defined as any untoward medical occurrence in a clinical study subject administered a pharmaceutical product, which does not necessarily have a causal relationship with the study IP. A treatment-emergent adverse event (TEAE) is defined as an AE that started or worsened in severity on or after the date of the IP administration (Day 1). All AEs will be coded using the Medical Dictionary for Regulatory Activities (MedDRA) Version 22.1 and will be summarized by System Organ Class (SOC) and Preferred Term (PT).

All adverse events will be graded using the Common Terminology Criteria for Analysis Events (CTCAE) Version 5.0, ranging from 1 to 5: Grade 1 (Mild), Grade 2 (Moderate), Grade 3 (Severe), Grade 4 (Life threatening or disabling), or Grade 5 (Death). If the grade is missing for a TEAE, the event will be counted as grade 3 in the summary tables.

Subjects will be observed for possible allergic reactions following the treatment and will be monitored for DLAEs throughout the study. All AEs, including SAEs, will be collected from the time of enrollment until 30 days after the treatment. Following the first 30 days, only SAEs that are at least possibly related to the treatment or study procedures will be collected.

An overall summary for subjects with AEs will be summarized by cohort (each dose level of JK07 and the placebo group pooled across all the treatment groups) including the following subsets. The number of events and subjects will be included.

- **AEs**
- **TEAEs**
- TEAEs related to study drug. This subset includes TEAEs with a drug relationship of “possibly related” and “definitely related”, or a missing drug relationship.
- Serious TEAEs
- Serious TEAEs related to study drug. This subset includes Serious TEAEs with a drug relationship of “possibly related” and “definitely related”, or a missing drug relationship.
- TEAEs leading to study drug permanent discontinuation
- TEAEs leading to study drug infusion interruption. This subset includes TEAEs with an answer “Yes” to the question “Was infusion interrupted?” on the Infusion Drug Administration form.
- Treatment-emergent infusion site reactions. This subset includes TEAEs with an answer “Yes” to the question “Was this an infusion site reaction?” on the AE form
- TEAES by maximum grade. Only present the number of subjects for this subset.

- **DLAEs**
- DLAEs related to study drug. This subset includes DLAEs with a drug relationship of “possibly related” and “definitely related”, or a missing drug relationship.
- Serious DLAEs
- Serious DLAEs related to study drug. This subset includes Serious DLAEs with a drug relationship of “possibly related” and “definitely related”, or a missing drug relationship.
- DLAEs leading to study drug permanent discontinuation
- DLAEs leading to study drug infusion interruption. This subset includes DLAEs with an answer “Yes” to the question “Was infusion interrupted?” on the Infusion Drug Administration form.
- DLAEs with infusion site reactions. This subset includes DLAEs with an answer “Yes” to the question “Was this an infusion site reaction?” on the AE form
- **SAEs**

In addition, summary tables will present the number and percentage of subjects and events by treatment group and overall, ordered by System Organ Class (SOC), Preferred Term (PT), and by the following classes, using the Safety Evaluation Population:

- SAEs
- SAEs having Infusion Site Reaction
- TEAEs
- TEAEs leading to study drug infusion interruption
- TEAEs leading to study drug permanent discontinuation
- TEAEs related to study drug
- TEAEs having Infusion Site Reaction
- DLAEs
- TEAEs by maximum severity (i.e. by CTCAE grading)
- TEAEs by maximum relationship to study drug

The DLAEs will be summarized by SOC and PT for the DLAE Evaluation Population.

At each level of summary of subject, a subject will be counted once if he/she reported one or more events. Specifically:

- For summary of TEAEs by severity, a subject will be classified according to the most severe event.
- For summary of TEAEs by relationship to study drug, a subject will be classified according to the closest relationship.

- For summary of SAEs by outcome, a subject will be classified according to the worst outcome.

For summary of TEAEs by action taken with study drug, a subject will be classified as “Drug Permanently Discontinued,” “Dose Interrupted,” “Other Action,” or “Dose Not changed.”

All AEs will be presented in a by-subject listing, detailing in the verbatim term given by the investigator, PT, SOC, start date, end date or ongoing, severity, seriousness, outcome, relationship to the study drug, and action taken. Treatment-emergent infusion site reactions, TEAEs leading to drug permanently discontinuation, and TEAEs related to study drug, DLAEs, SAEs, and deaths will be presented in separate listings respectively.

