Randomization u	X													

Abbreviations: 2D-TTE, 2-dimensional transthoracic echocardiography;  $\beta$ -hCG, beta-human chorionic gonadotrophin; CPK-MB, creatine kinase – muscle/brain; CPK, creatine phosphokinase; ECG, electrocardiogram; HbA1c, glycosylated hemoglobin; HDL, high density lipoprotein; hs-CRP, high-sensitivity C-reactive protein; ICD, implantable cardioverter-defibrillators; IP, investigational product; LDH, lactate dehydrogenase; LDL, low density lipoprotein; PK, pharmacokinetic.

a Subjects should be admitted in the hospital study unit by 7:00 AM, or as early as practicable, on Day 1. The subject should arrive fasted (at least 10-hour fast). All baseline clinical and laboratory assessments should be conducted prior to light breakfast/snack being provided to the subject. Subjects will be scheduled for discharge on the morning of Day 3.

b Subjects will be scheduled for hospital discharge on Day 3, after completion of all planned in-patient safety, PK, and exploratory PD/biomarker assessments. However, subjects may be asked to remain in the hospital study unit for more than 48 hours after the IP administration at the Investigator's discretion.

c A full physical examination will be performed at screening. An abbreviated physical examination will be conducted at all other visits. See [Section 8.2.1](#). During screening all subjects must verify they have no prior history of malignancy and/or have undergone cancer screening or undergo cancer screening according to American Cancer Society Guidelines ([Appendix 1 Cancer Screening Guidelines](#)).

d Women of childbearing potential only.  $\beta$ -hCG blood test at screening, urine dipstick test upon admission on Day 1 prior to IP administration to confirm absence of pregnancy, and urine specimens at all time points thereafter.

e See [Section 8.2.2](#) for assessment times and parameters.

fAll AEs, including SAEs will be collected from the time of study enrollment and until 30 days after the IP administration. Following the first 30 days, only SAEs deemed at least possibly related to the study drug or study procedures should be collected. Refer to [Table 9](#) for additional details.

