### 8.2 Safety Assessments

Planned time points for all safety assessments are provided in Table 1, and Table 2, and Appendix 3, Table 13 and Table 14.

Subjects will be observed for injection site reactions until Day 4 following IP administration, for DLAEs until Day 15 following IP administration, and for AEs and SAEs from the time of informed consent until 30 days after the IP administration. Following Day 30, only SAEs deemed at least possibly related to the study drug or study procedures will be collected until the End of Study visit (Day 180).

The safety of JK07 in patients with heart failure with reduced ejection fraction will be evaluated based on criteria described by the CTCAE Version 5.0.

The investigator will monitor the occurrence of all AEs during the first 30 days after administration of the study drug. All AEs must be recorded in the source documents and on the appropriate page(s) of the case report form. All SAEs including any deaths, which occur up to and including 30 days after administration of the study drug, must be reported to the Medical Monitor within one working day, whether or not considered causally related to the study drug. Following the first 30 days, only SAEs deemed at least possibly related to the study drug or study procedures should be collected and reported as such. All AEs and SAEs will be followed until resolution, stabilization, until the event is otherwise explained, until the end of their participation in the study, or until the subject is lost to follow-up.

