### **8.3.3      Time Period and Frequency for Collecting AE and SAE Information**

All AEs, including SAEs will be collected from the time of enrollment and until 30 days after the IP administration. Following the first 30 days, only SAEs deemed at least possibly related to the study drug or study procedures should be collected.

Medical occurrences that begin before the start of study treatment but after obtaining informed consent will be recorded on the Medical History/Current Medical Conditions section of the eCRF, not the AE section.

Investigators are not obligated to actively seek AEs or SAEs for subjects after their study participation ends. However, if the Investigator learns of any SAE, including a death, at any time after a subject has been discharged from the study, and he/she considers the event to be reasonably related to the study treatment or study participation, the Investigator must promptly notify the Sponsor.

All SAEs will be recorded on an SAE report form and reported to the Sponsor designee within 24 hours of the investigator's awareness of the event. The Investigator will submit any updated SAE data to the Sponsor

designee within 24 hours of the investigator's awareness of any follow-up information associated with the event.

SAE reports will be submitted to IQVIA Biotech Safety Management Department via one of the following methods:

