### **III. Study Endpoints**

#### **A. Primary**

- Incidence and severity of treatment-emergent adverse events (TEAEs) and their relationship to the investigational product (IP).
- 12-lead electrocardiogram (ECG) parameters (heart rate, PR, QRS, QT, QTcF) change from baseline derived as mean from triplicate ECG recording as well as QT and QTcF outlier analyses.
- Change from Baseline in the incidence of rhythm abnormalities (retrieved from telemetry readings for 48 hours postdose).
- Change from Baseline in Laboratory parameters (hematology, chemistry, coagulation, and lipid panels)
- Immunogenicity:
  - Incidence of early and delayed-type hypersensitivity responses
  - Presence of serum anti-JK07 antibodies (confirmed positive antibody response, titer, neutralizing antibodies)
- Change from Baseline in Vital Signs (Blood Pressure, Temperature, Heart Rate, Respiratory Rate)

- Relationship between Vital Signs (Blood Pressure, Temperature, Heart Rate, Respiratory Rate) and JK07, comparing with relationship between Vital Signs and Placebo

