### **D. Missing Data**

Unless stated below, no imputation will be performed on missing safety and efficacy data. Missing data are simply noted as missing or “-” in tables and listings. If a baseline value is missing, change from baseline will not be calculated.

*Missing or Partial Heart Failure Diagnosis Date.* Partial heart failure diagnosis dates will be imputed in order to calculate the disease duration.

- A completely missing diagnosis date will not be imputed.

- A heart failure diagnosis date missing the month and day will be imputed as Jan 1st of the year.
- A heart failure diagnosis date missing the day will be imputed as the 1st of the month.

*Missing Dates in Adverse Events form and Concomitant Medications form.* Every effort will be made to avoid missing/partial dates in on-study data including AE and medication start and stop dates. Dates from these forms will be reported in listings as collected.

AEs that cannot be definitely determined as occurring prior to study IP administration will be counted as treatment-emergent adverse events (TEAEs) unless either the partial start date or a partial or complete end date documents the AE as occurring prior to treatment. Partial dates of AEs will be imputed as follows:

- Completely missing start date will not be imputed, and the event will be considered treatment-emergent unless the answer to “Did the event occur during or after study drug infusion?” is “No, event is not treatment emergent” on the Adverse Events CRF form.
- Start date missing both the month and day will be imputed as:
  - The IP administration date if the year of the start date is the same as that of the IP administration date.
  - Otherwise, Jan 1st of the year of the start date will be used.
- Start date missing the day will be imputed as:
  - The IP administration date if the year and month of the start date are the same as that of the IP administration date.
  - Otherwise, the 1st day of the month of the start date will be used.
- Partial or missing AE stop dates will not be imputed.

If the answer to “Did the event occur during or after study drug infusion?” is “Yes, event is treatment emergent” on the Adverse Events CRF form, the event will be considered treatment-emergent.

Partial dates entered on the Concomitant Medications (CM) form will be imputed as follows, for the purposes of determining whether the record is a prior or concomitant medication:

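### AEs that the site marks as pre-infusion still count as TEAEs when they are dated, or imputed, to Day 1

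*SAP*

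**What the plan says.** **Endpoint and definition.** The first primary endpoint in SAP III.A is "Incidence and severity of treatment-emergent adverse events (TEAEs) and their relationship to the investigational product (IP"). SAP VII.B takes a TEAE to be an event "defined as an AE that started or worsened in severity on or after the date of the IP administration (Day 1"). No clock time is mentioned.

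**Use of the CRF question.** The AE form asks whether the event occurred during or after the infusion. In SAP V.D the negative answer appears in one bullet only: "Completely missing start date will not be imputed, and the event will be considered treatment-emergent unless the answer to" that question is "No, event is not treatment emergent". A positive answer makes any event treatment-emergent. There is no matching general rule for a negative one.

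**Partial start dates.** Where only the day is missing, the imputed date is "The IP administration date if the year and month of the start date are the same as that of the IP administration date". The same is done on the year alone if the month is missing too. The sentence that introduces these rules accepts a partial start date, or a partial or complete end date, as proof that an event came before treatment. It does not list the CRF answer.

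**Pre-dose period and AE collection.** Protocol Table 1, footnote a, has subjects admitted by about 7:00 AM on Day 1 and adds: "All baseline clinical and laboratory assessments should be conducted prior to light breakfast/snack being provided to the subject". Protocol Table 2 places an ECG, blood and urine sampling and an echocardiogram before the infusion. Protocol 8.2 observes subjects "for AEs and SAEs from the time of informed consent until 30 days after the IP administration". Protocol 8.3.3 says that occurrences beginning after consent but before study treatment "will be recorded on the Medical History/Current Medical Conditions section of the eCRF, not the AE section".

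**The concern.** Day 1 holds several hours of procedures before any drug is given. An event in those hours shares its date with the infusion, so a date-only rule cannot separate the two. The item that can separate them is the site's direct answer on the AE form, and the SAP trusts that answer when the date is wholly missing but not when the date is Day 1. Neither the Protocol 8.3.7 list of AE items nor the AE listing in SAP VII.B mentions a time of onset. As far as the documents show, the CRF answer is therefore the only AE item that distinguishes before from after within Day 1.

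A misclassified event passes into the TEAE tables by grade, relationship and seriousness. SAP VII.B also counts a missing grade as Grade 3 and a missing relationship as related. A pre-dose event with blanks could therefore be tabulated as a related Grade 3 TEAE in a particular dose group.

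**Working it through.** The plan states no figure on this point, so there is nothing to reproduce. The check applies the SAP rules to each combination of start date and CRF answer, then works out the weight of one subject.

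**Step 1. Classification under SAP V.D and VII.B as written**

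| Start date | CRF 'Yes' | CRF 'No' | 'No', with an end date before treatment |
|---|---|---|---|
| Complete, before Day 1 | TEAE | not TEAE | not TEAE |
| Complete, Day 1 | TEAE | **TEAE** | cannot arise |
| Complete, after Day 1 | TEAE | TEAE | cannot arise |
| Partial, imputed to the dosing date | TEAE | **TEAE** | not TEAE |
| Wholly missing | TEAE | not TEAE | not TEAE |

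The two bold cells are the defect: the site has said the event was pre-infusion and the SAP counts it anyway. In the Day 1 row an end date cannot help, because an event starting on Day 1 cannot end before it. The cell for a complete date after Day 1 with 'No' is a data conflict. Keeping that event as a TEAE is the cautious choice. (The table sets aside worsening after dosing, which makes an event a TEAE in any row.)

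**Step 2. Can such events be on the AE form?** Protocol 8.3.3 sends pre-treatment occurrences to medical history. Three things point the other way:
- Protocol 8.2 collects AEs from consent.
- The AE form offers an answer meaning not treatment-emergent.
- SAP VII.B counts AEs separately from TEAEs.

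Some pre-dose events must therefore be expected on the form. The documents give no number.

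**Step 3. Weight of one subject.** Each subject counts once at each level of summary (SAP VII.B), so incidence moves only if the affected subject has no other TEAE. The shift is then 100/n percentage points.

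A 5-subject cohort has 1 sentinel and 3:1 randomization. A 9-subject cohort has 1 sentinel and 6:2 (Protocol 1.1 and 4.2). SAP V.K limits the Safety Evaluation Population to randomized subjects, and sentinels are not randomized.

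| JK07 group | Randomized only | With sentinel |
|---|---|---|
| 5-subject cohort | 100/3 = 33.3 | 100/4 = 25.0 |
| 9-subject cohort | 100/6 = 16.7 | 100/7 = 14.3 |

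For pooled placebo the range runs from five cohorts with one placebo subject each (100/5 = 20.0) to seven cohorts with two each (100/14 = 7.1).

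**The case against.** The case against has real force.

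- **Protocol 8.3.3.** It turns on the start of treatment rather than the date, so it covers the pre-dose hours of Day 1. If sites follow it, most of these events never reach the AE form. SAP precedence over the protocol governs analysis and cannot put them there. This stands, and it makes the number small. It does not make it zero, for the reasons in step 2 of the working.
- **Intent.** The sentence introducing the AE date rules in SAP V.D refers to events that cannot definitely be placed before IP administration, which suggests that known pre-dose events were meant to be left out. But it sits under missing dates and accepts only dates as proof, so it does not alter VII.B for a complete Day 1 date.
- **Partial dates.** A reader might infer that every partly dated screening event in the dosing month becomes a TEAE. It does not: an end date before treatment excludes it.
- **Subsets.** A reader might infer that pre-dose cannula pain inflates infusion-site reactions, or that pre-dose ectopy inflates arrhythmias. Protocol 8.2.2 makes an AE only of a site reaction greater than an IV line would normally cause. SAP VII.H analyses telemetry from administration onwards, and Protocol 8.3.7 sets criteria before an abnormal finding becomes an AE. These examples do not carry the point.
- **Consequence.** The study is descriptive, all AEs are listed, and related TEAEs are tabulated separately. Under Protocol 8.3.12 the DRC judges whether AEs are TEAEs or DLAEs. This limits the harm. It does not correct the rule that produces the primary tables.

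**Conclusion.** The point holds in a narrow form. The SAP classifies as treatment-emergent an AE-form event that the site has marked as pre-infusion if it is dated Day 1, or if it is partly dated, imputed to Day 1 and has no end date showing that it came earlier. Events dated before Day 1 and wholly undated events marked 'No' are already handled correctly.

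The number affected is unknown and probably small, assuming that sites mostly follow Protocol 8.3.3. Where it happens to a subject with no other TEAE, it shifts a JK07 group's incidence by 14.3 to 33.3 points, depending on cohort size and on whether sentinels count.

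A reader might go further and infer that the rule hides a safety signal, or that pre-dose events enter the endpoint routinely. The documents support neither. The rule only adds events, in both arms, and no event after dosing is lost. What remains is a primary-endpoint definition that disregards the more direct information already collected.

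**What to change.** In SAP VII.B and V.D:

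- Define a TEAE as an AE whose onset, or whose worsening, falls at or after the start of the infusion.
- For a start date of Day 1, or one imputed to Day 1, let the CRF answer 'No' make the event not treatment-emergent, unless it worsened after the infusion began.
- Keep date precedence for a complete start date after Day 1, and query any 'No' on such an event. The CRF answer should not decide in every case: a mistaken 'No' would then drop an event clearly dated after dosing.
- Keep the present inclusive rule when the CRF answer is missing.

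Reconcile Protocol 8.2 with 8.3.3 on where pre-dose events are recorded.

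The cost is a few sentences in the SAP, one programming condition and a data query. The CRF item is already collected, trial conduct does not change, and SAP I.B allows changes to the plan until database lock.

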### **8.3.7      Recording AEs and SAEs**

When an AE/SAE occurs, it is the responsibility of the Investigator to review all documentation (e.g., hospital progress notes, laboratory reports, and diagnostics reports) related to the event.

The Investigator will then record all relevant AE/SAE information in the eCRF. Each event must be recorded separately.

It is not acceptable for the Investigator to send photocopies of the subject's medical records in lieu of completion of the AE/SAE eCRF page. There may be instances when copies of medical records for certain cases are requested. In this case, all subject identifiers, except for the subject number, will be redacted on the copies of the medical records before provided.

Each AE is to be evaluated for:

- AE diagnosis or syndrome (if not known, signs or symptoms)
- Dates of onset and resolution
- Severity (including grade changes as per the CRF completion guidelines)
- Causal relationship with study drug or protocol-mandated procedures
- Seriousness
- Action taken
- Outcome

Whenever possible, a unifying diagnosis should be reported as opposed to a listing of individual symptoms. However, symptoms should be grouped into a diagnosis only if each sign or symptom is a medically confirmed component of that diagnosis as evidenced by current standard medical textbooks. If any aspect of a sign or symptom does not fit into a classic pattern of the diagnosis, the individual symptom should be reported as a separate AE.

A preexisting medical condition is one that is present during the screening period for this study. Such conditions should be recorded as General Medical History and Baseline Conditions. A preexisting medical condition should be recorded as an AE only if the frequency, severity, or character of the condition worsens during the study.

For hospitalizations or surgical or diagnostic procedures, the illness leading to the surgical or diagnostic procedure should be recorded as the SAE, not the procedure itself. The procedure should be captured in the narrative as part of the action taken in response to the illness.

When reporting an SAE of progression of the disease under investigation, specific manifestations of the progression (e.g., acute coronary syndrome, acute pulmonary edema) should be reported, rather than the general term "disease progression."

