### **B. Purpose of the Statistical Analysis Plan**

This Statistical Analysis Plan (SAP) is based on the JK07.1.01 study Protocol Amendment 3.0, providing additional details concerning the statistical analyses outlined in the protocol and reflecting any changes to the protocol.

This SAP will govern the analysis of data from this study. This plan contains definitions of analysis populations, derived variables, data handling rules, format of data presentation and statistical methods for the safety, pharmacokinetic (PK), and pharmacodynamic (PD) analyses. The plan may be modified until the time of database lock. The database will be locked after medical/scientific review of the data has been completed, protocol deviations have been identified, and the data have been declared clean. The purpose of the SAP is to ensure the credibility of the study findings by pre-specified statistical approaches to the study data prior to the database lock. This plan will not repeat all the definitions given in the protocol but will provide further details of summaries and analyses planned therein. Any deviations from the analysis plan, including any after the time of database lock, will be documented as such in the study report. Table, Listing, and Figure (TLF) shells are provided in a separate, accompanying document. The SAP will take precedence over the protocol.

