### **B. Definition of Baseline**

This is a single-dose study. Unless otherwise specified, baseline is defined as the last non-missing measurement prior to study IP administration. Change from baseline will be calculated as post-baseline values minus baseline values.

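### The SAP's subsets of TEAEs and DLAEs leading to infusion interruption are selected by a per-subject answer, so an interrupted subject's unrelated events are counted too

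*SAP*

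**What the plan says.** The overall AE summary in SAP VII.B (Adverse Events) counts events and subjects in a series of named subsets. One reads "TEAEs leading to study drug infusion interruption. This subset includes TEAEs with an answer" of yes to the question on the Infusion Drug Administration form that asks whether the infusion was interrupted. The DLAE block repeats the construction: "DLAEs leading to study drug infusion interruption. This subset includes DLAEs with an answer" of yes to the same question on the same form. No further condition is given on onset relative to the interruption, the recorded reason, action taken, or a link to a particular AE. The TEAE class appears again in the list of SOC/PT tables, without another definition.

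The neighbouring items differ. The next subset is "Treatment-emergent infusion site reactions. This subset includes TEAEs with an answer" of yes to a question on the AE form itself. "TEAEs leading to study drug permanent discontinuation" is listed with no derivation, as is its DLAE counterpart. Further on, the SAP states: "For summary of TEAEs by action taken with study drug, a subject will be classified as" one of four categories, among them interrupted and permanently discontinued.

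Three other statements bear on the point:
- SAP V.B says "This is a single-dose study", and Protocol 6.6 agrees.
- SAP I.B says "This SAP will govern the analysis of data from this study", and gives the SAP precedence over the protocol.
- Protocol 8.3.7 says "Each AE is to be evaluated for" a set of items that includes action taken. SAP VII.B carries action taken into the by-subject AE listing, and SAP VII.A lists the reason for any interruption.

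**The concern.** The name of the subset is causal, but the sentence that defines it is not. It asks only whether the infusion was interrupted, and with a single infusion the answer is shared by every AE the subject has. A programmer following the definition would merge a subject-level flag onto all of that subject's events.

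Three descriptive displays are exposed: the TEAE and DLAE interruption rows of the overall AE summary, and the SOC/PT table of TEAEs leading to interruption. Tolerability is part of the primary objective and the dose groups are very small, so one subject or a few preferred terms placed there in error can change how a dose level reads. The report could also show two different interruption counts, one from these rows and one from the action-taken summary, with no rule to reconcile them.

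**Working it through.** The plan gives no figure to reproduce. The check applies the rule as written.

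**Inputs**
- One infusion per subject (SAP V.B, Protocol 6.6).
- A TEAE starts or worsens on or after the dosing date. All AEs are collected to 30 days, then only SAEs at least possibly related to treatment or study procedures (SAP VII.B). Events that begin long after the infusion therefore qualify.
- Events and subjects are both counted (SAP VII.B).
- The documents give no interruption rate, so the event counts below are assumed.

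**Event count.** Let an interrupted subject have k TEAEs, of which c led to the interruption (0 ≤ c ≤ k). The value of c can exceed 1, because Protocol 8.3.7 has symptoms that do not fit a diagnosis reported as separate AEs. The flag does not vary within the subject, so:
- count under the rule = k
- count the label calls for = c
- excess = k − c

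| k | Rule reports | Excess, any c | Excess if an AE was the cause (c ≥ 1) | Excess if no AE was the cause (c = 0) |
|---|---|---|---|---|
| 1 | 1 | 0 to 1 | 0 | 1 |
| 3 | 3 | 0 to 3 | 0 to 2 | 3 |
| 5 | 5 | 0 to 5 | 0 to 4 | 5 |

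For DLAEs the same formula gives an excess of 0 to 1 with one DLAE and 0 to 2 with two. Protocol 4.6 lists failure to deliver the full dose through possible treatment-related toxicity as a possible DLAE. If the causal event is itself a DLAE, the excess falls to 0 and 0 to 1.

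**Subject count.** The rule counts the subject when k ≥ 1; the label requires c ≥ 1. They differ only when c = 0 and k ≥ 1. That case is plausible. Protocol 6.1 has every interruption and stop/restart recorded, whatever the cause, and does not allow a restart once an infusion has had to be stopped for an AE. A protocol-compliant infusion that was interrupted and resumed was therefore not one that had to be stopped for an AE.

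**Weight of one wrongly counted subject**
- JK07: the Safety Evaluation Population requires randomization (SAP V.K) and sentinels are not randomized (SAP IV.D). That leaves 3 per cohort at 3:1 or 6 at 6:2, so 1/3 = 33.3% or 1/6 = 16.7%. If sentinels were analysed as well, 1/4 = 25.0% or 1/7 = 14.3%.
- Pooled placebo (SAP V.M): five cohorts × 1 = 5, so 1/5 = 20.0%; seven cohorts × 2 = 14, so 1/14 = 7.1%. With fewer than five cohorts at 3:1, the share would exceed 20.0%.

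**The case against.** The strongest reply is that the subset's name already restricts it to events leading to an interruption, and that the sentence speaks of TEAEs with an answer, not of all TEAEs in subjects with an answer. If the CRF links an AE to the infusion form, the rule could work as intended. The CRF and the table shells are not among the documents, so such a link cannot be excluded. That limit stands. But the SAP names no such field, and the infusion-site-reaction subset shows that it does name an event-level question where it relies on one.

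A second reply is that the information can be recovered elsewhere: an action-taken summary by subject, an AE listing with start date and action taken, and an exposure listing with the reason for interruption. In cohorts of 5 to 9 a stray entry could be traced. That is true, but none of these corrects the two rows or the SOC/PT table. They show instead that a suitable event-level source exists.

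Third, the consequences are modest. The displays are descriptive, total TEAE incidence does not change, and nothing in the documents makes this subset an input to a Data Review Committee decision. All of that stands and limits the weight of the point. The missing derivation for permanent discontinuation is, taken alone, mostly a lack of detail; the action-taken category suggests the natural derivation.

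**Conclusion.** The concern holds. As written, the rule cannot separate events that led to an interruption from the subject's other events. It miscounts events as soon as an infusion is interrupted in a subject who also has an event that did not lead to the interruption. The excess is k − c events per interrupted subject. The subject count is also wrong when no AE was the cause and the subject has at least one TEAE.

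If no infusion is interrupted, the effect is zero. The conclusion rests on one infusion per subject and on the absence of an AE-link field in the SAP. The event counts are illustrative, and the percentages depend on the cohort sizes and numbers stated with them. This should be corrected before database lock, but it does not threaten the study's main safety summaries.

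**What to change.** In SAP VII.B, count a TEAE or DLAE as leading to interruption only if it is identified at event level as a cause. Use the AE record's action taken with study drug or, if the CRF has one, a named AE-link field. Before database lock, check the selected events against the infusion form's answer and the recorded reason for interruption, and resolve any mismatch. Keep the infusion-form answer alone for the exposure listing. Apply the same definition to the SOC/PT table.

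Give the permanent-discontinuation subsets a stated derivation as well. Say in the analysis definition to which subset an event belongs when the infusion was stopped for it and not restarted, so that such events are neither lost nor counted twice. This concerns classification in the tables only.

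The cost is a few sentences in the SAP and reprogramming of two summary rows and one table. Action taken and the reason for interruption are already named in the documents; the response options on the AE form need a check against the CRF. SAP I.B allows changes until database lock. After that, any departure has to be documented in the study report.
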